10.8.3. Medical monitor, GCSP Physician and PI actions for Restart following VSLC decision

10.8.3.1. Medical Monitor and GCSP Physician Actions

- Medical Monitor must notify PI of VSLC’s restart decision and recommended dosing regimen in writing and Medical Monitor must record note in study files.
- The Safety Review Team must record restart outcomes and the GCSP Physician must send these to the VSLC (see template below).
- All severe reactions (associated with bilirubin>2xULN or jaundice, or INR≥1.5), SAEs or fatalities which occur following a drug or restart. must be immediately

reported to Line Management including, VSLC Chair, VP Global Medical Strategy and EU Qualified Person for Pharmacovigilance.

10.8.3.2. PI Actions:

- The PI must obtain Ethics Committee or Institutional Review Board approval of drug restart, as required.
- If VSLC approves drug restart, the patient must sign a new informed consent containing a clear description of possible benefits and risks of drug administration including recurrent, more severe liver injury or possible death.
- *Targeted drug drug restart consent form must be used.*
- The patient’s informed consent must be recorded in the study chart, and the drug administered at agreed dose, as communicated by Medical Monitor.
- Liver chemistries must be followed *once weekly for ‘restart’ cases* for a minimum of one month and thereafter for as long as clinically indicated following drug re-initiation. If participant exhibits protocol-defined liver chemistry elevations, IP should be discontinued as protocol specified.
- Medical Monitor and the Ethics Committee or Institutional Review Board must be informed of the patient’s outcome following drug restart.

Drug Restart Outcomes Table Template

[figure not shown]
To be completed/updated and provided to VSLC with each event recorded across studies and indications

Drug Restart Outcomes Table – Update with each event

Protocol#	Participant#	Restart?	Safety outcome*	Drug benefit

Restart safety outcomes:

CCI - This section contained Clinical Outcome Assessment data collection questionnaires or indices, which are protected by third party copyright laws and therefore have been excluded.

10.9. Appendix 9: AEs, ADEs, SAEs, SADEs, USADEs and Device Deficiencies: Definition and Procedures for Recording, Evaluating, Follow-up, and Reporting in Medical Device Studies

- The definitions and procedures detailed in this appendix are in accordance with ISO 14155 and the European Medical Device Regulation (MDR) 2017/745 for clinical device research (if applicable).
- Both the investigator and the sponsor will comply with all local medical device reporting requirements for medical devices.
- The detection and documentation procedures described in this protocol apply to all GSK medical devices provided for use in the study (see Section 6.1.3 for the list of GSK medical devices).

10.9.1. Definition of Medical Device AE and ADE

Medical Device AE and ADE Definition

- A medical device AE is any untoward medical occurrence, in a clinical study participant, users, or other persons, temporally associated with the use of study intervention whether or not considered related to the investigational medical device. An AE can therefore be any unfavorable and unintended sign (including an abnormal laboratory finding), symptom, or disease (new or exacerbated) temporally associated with the use of an investigational medical device. This definition includes events related to the investigational medical device or comparator and events related to the procedures involved except for events in users or other persons, which only include events related to investigational devices.
- An adverse device effect (ADE) is defined as an AE related to the use of an investigational medical device. This definition includes any AE resulting from insufficient or inadequate instructions for use, deployment, implantation, installation, or operation, or any malfunction of the investigational medical device as well as any event resulting from use error or from intentional misuse of the investigational medical device.

10.9.2. Definition of Medical Device SAE, SADE and USADE

A Medical Device SAE is any serious adverse event that:

- a. Led to death
- b. Led to serious deterioration in the health of the participant, that either resulted in:
 - A life-threatening illness or injury. The term 'life-threatening' in the definition of 'serious' refers to an event in which the participant was at risk of death at the time of the event. It does not refer to an event, which hypothetically might have caused death, if it were more severe.
 - A permanent impairment of a body structure or a body function.
 - Inpatient or prolonged hospitalization. Planned hospitalization for a pre-existing condition, or a procedure required by the protocol, without serious deterioration in health, is not considered an SAE.
 - Medical or surgical intervention to prevent life-threatening illness or injury or permanent impairment to a body structure or a body function
 - Chronic disease (MDR 2017/745).
- c. Led to fetal distress, fetal death or a congenital abnormality or birth defect
- d. Is a suspected transmission of any infectious agent via a medicinal product

Serious adverse device effect (SADE) definition

- A SADE is defined as an adverse device effect that has resulted in any of the consequences characteristic of an SAE.
- Any device deficiency that might have led to an SAE if appropriate action had not been taken, intervention had not occurred, or circumstances had been less fortunate.

Unanticipated serious adverse device effect (USADE) definition

- An USADE (also identified as UADE in US Regulations 21 CFR 813.3), is defined as a serious adverse device effect that by its nature, incidence, severity or outcome has not been identified in the current version of the risk analysis report

10.9.3. Definition of Device Deficiency**Device Deficiency Definition**

- A device deficiency is an inadequacy of a medical device with respect to its identity, quality, durability, reliability, safety, or performance. Device deficiencies include malfunctions, use errors, and inadequacy of the information supplied by the manufacturer.

10.9.4. Recording and Follow-Up of AE and/or SAE and Device Deficiencies**AE, SAE and Device Deficiency Recording**

- When an AE/SAE/device deficiency occurs, it is the responsibility of the investigator to review all documentation (e.g., hospital progress notes, laboratory reports, and diagnostics reports) related to the event.
- The investigator will then record all relevant AE/SAE/device deficiency information in the participant's medical records, in accordance with the investigator's normal clinical practice, and on the appropriate form.
- It is **not** acceptable for the investigator to send photocopies of the participant's medical records to GSK and ViiV in lieu of completion of the GSK/AE/SAE/device deficiency form.
- There may be instances when copies of medical records for certain cases are requested by GSK or ViiV. In this case, all participant identifiers, with the exception of the participant number, will be redacted on the copies of the medical records before submission to GSK.
- The investigator will attempt to establish a diagnosis of the event based on signs, symptoms, and/or other clinical information. Whenever possible, the diagnosis (not

the individual signs/symptoms) will be documented as the AE/SAE.

- For device deficiencies, it is very important that the investigator describes any corrective or remedial actions taken to prevent recurrence of the deficiency.
 - A remedial action is any action other than routine maintenance or servicing of a medical device where such action is necessary to prevent recurrence of a device deficiency. This includes any amendment to the device design to prevent recurrence.

Assessment of Intensity

- The investigator will make an assessment of intensity for each AE/SAE/device deficiency reported during the study and assign it to one of the following categories:
 - Mild: Asymptomatic or mild symptoms; clinical or diagnostic observations only; intervention not indicated.
 - Moderate: Minimal, local or noninvasive intervention indicated; limiting age-appropriate instrumental Activities of Daily Living (ADL). Instrumental ADL refers to preparing meals, shopping for groceries or clothes, using the telephone, managing money, etc.
 - Severe: Severe or medically significant but not immediately life-threatening; hospitalization or prolongation of hospitalization indicated; disabling, limiting self care ADL. Self care ADL refers to bathing, dressing and undressing, feeding self, using the toilet, taking medications, and not bedridden.

Assessment of Causality

- The investigator is obligated to assess the relationship between study intervention and each occurrence of each AE/SAE/device deficiency. The investigator will use clinical judgment to determine the relationship.
- A *reasonable possibility* of a relationship conveys that there are facts, evidence, and/or arguments to suggest a causal relationship, rather than a relationship cannot be ruled out.
- Alternative causes, such as underlying disease(s), concomitant therapy, and other risk factors, as well as the temporal relationship of the event to study intervention administration will be considered and investigated.
- The investigator will also consult the Investigator's Brochure (IB) or Product Information, for marketed products, in his/her assessment.
- For each AE/SAE/device deficiency, the investigator **must** document in the medical notes that he/she has reviewed the AE/SAE/device deficiency and has provided an assessment of causality.
- There may be situations in which an SAE has occurred and the investigator has

minimal information to include in the initial report to GSK. However, it is very important that the investigator always make an assessment of causality for every event before the initial transmission of the SAE data to GSK.

- The investigator may change his/her opinion of causality in light of follow-up information and send an SAE follow-up report with the updated causality assessment.
- The causality assessment is one of the criteria used when determining regulatory reporting requirements.

Follow-up of AE/SAE/device deficiency

- The investigator is obligated to perform or arrange for the conduct of supplemental measurements and/or evaluations as medically indicated or as requested by GSK to elucidate the nature and/or causality of the AE/SAE/device deficiency as fully as possible. This may include additional laboratory tests or investigations, histopathological examinations, or consultation with other health care professionals.
- If a participant dies during participation in the study or during a recognized follow-up period, the investigator will provide GSK with a copy of any post-mortem findings including histopathology.
- New or updated information will be recorded in the originally completed form.
- The investigator will submit any updated SAE data to GSK within 24 hours of receipt of the information.

10.9.5. Reporting of SADEs

SADE Reporting to GSK

- **NOTE:** There are additional reporting obligations for medical device deficiencies that are potentially related to SAEs that must fulfil the legal responsibility to notify appropriate regulatory authorities and other entities about certain safety information relating to medical devices being used in clinical studies.
- Any device deficiency that is associated with an SAE must be reported to the manufacturer of the device (if known) within 24 hours after the investigator determines that the event meets the definition of a device deficiency.

10.10. Appendix 10: Recommendation for Assessment of Waist Circumference, Hip Circumference and Weight (Adapted from WHO STEPS Surveillance Manual, 2017) and for Resting Blood Pressure

10.10.1. Waist Circumference

Equipment

To take waist circumference measurements you will need a:

- Constant tension tape (for example, Figure Finder or Myo Tape Body Tape Measure);
 - Tape measures will be provided for the study
- Chair or coat stand for participants to place their clothes.

Privacy

A private area is necessary for this measurement. This could be a separate room, or an area that has been screened off from other people.

Preparing the participant

This measurement should be taken without clothing, meaning, directly over the skin.

[figure not shown]
If this is not possible, the measurement may be taken over light clothing (for example, a hospital gown, an undergarment or thin t-shirt). Thick or bulky clothing must be removed. Body shaping garments are not allowed to be worn during this measurement.

How to take the measurement

We recommend having the same study staff performing the measurement across visits for individual study participants.

This measurement should be taken:

- at the end of a normal expiration;
- with the arms relaxed at the sides;
- at the midpoint between the lower margin of the last palpable rib and the top of the iliac crest (hip bone) ([Figure 8](#)).

Figure 8 Location of Midpoint for Waist Circumference Measurement**Procedure**

Follow the steps below to measure the waist circumference of a participant:

1. Standing to the side of the participant, locate the last palpable rib and the top of the hip bone. You may ask the participant to assist you in locating these points on their body.
2. Wrap the tension tape around the participant and position the tape at the midpoint of the last palpable rib and the top of the hip bone, making sure to wrap the tape over the same spot on the opposite side.

Note: Check that the tape is horizontal across the back and front of the participant and as parallel with the floor as possible.

3. Ask the participant to:
 - stand with their feet together with weight evenly distributed across both feet;
 - hold the arms in a relaxed position at the sides;
 - breathe normally for a few breaths, then make a normal expiration.

4. Measure waist circumference and read the measurement at the level of the tape to the nearest 0.1 cm, making sure to keep the measuring tape snug but not tight enough to cause compression of the skin.
 5. Record the measurement, in **centimetres to one decimal place**, within the eCRF.
- ***Note: Measure once and record.***

10.10.2. Hip Circumference

Equipment

To take hip circumference measurements you will need a:

- Constant tension tape (for example, Figure Finder or Myo Tape Body Tape Measure);
 - Tape measures will be provided for the study
- Chair or coat stand for participants to place their clothes.

Privacy

A private area is necessary for this measurement. This could be a separate room, or an area that has been screened off from other people. Hip measurements are taken immediately after waist circumferences.

Preparing the participant

This measurement should be taken without clothing, that is, directly over the skin.

If this is not possible, the measurement may be taken over light clothing (for example, a hospital gown or an undergarment). Thick or bulky clothing must be removed. Body shaping garments are not allowed to be worn during this measurement.

How to take the measurement

We recommend having the same study staff performing the measurement across visits for individual study participants.

This measurement should be taken:

- with the arms relaxed at the sides
- at the maximum circumference over the buttocks.

Procedure

Follow the steps below to take hip circumference measurements.

1. Stand to the side of the participant and wrap the tension tape around them.
2. Position the measuring tape around the maximum circumference of the buttocks.

3. Ask the participant to:
 - Stand with their feet together with weight evenly distributed over both feet;
 - Hold their arms relaxed at the sides.
4. Check that the tape position is horizontal all around the body and snug without constricting.
5. Measure hip circumference and read the measurement at the level of the tape to the nearest 0.1 cm.
6. Record the measurement, in **centimetres to one decimal place**, within the eCRF.

Note: Measure once and record.

10.10.3. Weight

Equipment

To measure weight, you will need a weighing scale, (such as a Tanita BC-587 or Tanita BC-730 scale). Alternatively, a BMI scale measuring both height and weight (e. g. Growth Management Scale) can be used.

Ensure the scale has been regularly calibrated according to the manufacturer instructions and that calibration documentations are filed and available to the study CRA as required.

We recommend using the same scale across visits for individual study participants.

We recommend having the same study staff performing the measurement across visits for individual study participants.

We recommend that the time of day a participant's weight is measured is consistent for every participant at the site within the study. (ex. If measured at 10 a.m. at initial measurement, attempt to have the participant measured at 10 a.m. at subsequent visits).

Set up requirements

Make sure the scales are placed on a firm, flat surface. Do not place the scales on:

- carpet
- a sloping surface
- a rough, uneven surface.

Set up scales

Follow the steps below before measuring the weight of a participant:

1. Make sure the scale is on a firm, flat surface.
2. Turn on the scale and wait until the display shows 0.0.

Procedures

Follow the steps below to measure the weight of a participant:

1. Ask the participant to remove their footwear (shoes, slippers, sandals, etc). They should also take off any heavy belts and remove all objects out of their pockets (example: mobile phones, wallets, coins).
2. Ask the participant to step onto scale with one foot on each side of the scale.
3. Ask the participant to:
 - stand still
 - face forward
 - place arms on the side and
 - wait until asked to step off.

Record the weight in **kilograms to one decimal place** in the eCRF.

References

[WHO STEPS Surveillance Manual, 2017; 3-5-9 to 3-5-13.]

10.10.4. Resting Blood Pressure

General instructions

- Ensure that healthcare professionals taking blood pressure measurements have adequate initial training and periodic review of their performance.
- Healthcare providers must ensure that devices for measuring blood pressure are properly validated, maintained and regularly recalibrated according to manufacturers' instructions.
- When measuring blood pressure in the clinic or in the study site, standardise the environment and provide a relaxed, temperate setting, with the person quiet and seated, and their arm outstretched and supported. Use an appropriate cuff size for the person's arm.
- Measure the blood pressure in one arm (in semi-supine* position or seated after 5 minutes rest).

*Semi-supine position: Laying /sitting back (at 45° angle or variations) in a relaxed position with feet touching a flat surface.

10.11. Appendix 11: COVID-19 Pandemic and Clinical Trial Continuity

Background

The COVID-19 pandemic presents significant logistical challenges for many clinical sites around the world, with variable restrictions being placed on site resources and operations, and on an individual participants ability to attend clinic visits. In some places, medical visits are occurring, and in others, research clinics are operating with only emergency staff.

Based on these challenges, it may be necessary to adopt additional measures and procedures to protect participant safety, and to ensure that there are no gaps in HIV-1 treatment for participants enrolled in this clinical study, through continuous access to antiretroviral therapy.

In order to maintain the scientific integrity of the study, and adhere to updated guidance from regulators, procedures have also been put into place to ensure that the actions taken to mitigate against any impact of COVID-19 are well documented in the trial database.

A “Memo to Investigators” was issued on March 18th, 2020 and served as a record of approved emergency actions being taken within this clinical trial to manage issues related to COVID-19. That memo continues to serve as record of approved actions which can be fully implemented by Investigators, in advance of this protocol guidance. This appendix will remain consistent with the guidance provided within the “Memo to Investigators” and will also serve to provide additional protocol documentation requirements and procedures.

This appendix outlines the measures which are approved for implementation within this clinical trial, to protect patient safety and to ensure the integrity of the clinical trial, as a result of COVID-19 only. These measures may be implemented in accordance with any requirements and expectations set out by local Independent Review Boards/Independent Ethics Committees and National Competent Authorities, as necessary.

This appendix **does not** apply to participant management issues that are unrelated to a specific, and documented, impact from COVID-19.

10.11.1. Changes to Study Visits and Study Procedures

- Where site staff resource is constrained due to COVID-19, IM dosing visits may proceed with limited or no other protocol-defined assessments (e.g. lab tests, questionnaires, etc.). If lab tests will be missed for more than one consecutive visit, the medical monitor must be contacted, to provide guidance for safety monitoring.
- For WOCBP, point of care pregnancy testing should be performed, prior to IM dosing.
- If central laboratory testing cannot be performed at a particular visit, and monitoring for safety is required, tests may be performed at an appropriately

authorised/accredited local laboratory (or other relevant clinical facility), if this can be done within local restrictions on physical distancing. The site should proactively inform the sponsor about such instances. Local laboratory results may be used to inform safety decisions. Results should be retained in source records.

- When on-site visits are reduced, it is important that the investigator continue collecting relevant clinical information, including adverse events, from the participant through alternative means, e.g. by telephone contact.
- There may be cases where the current principal investigator (PI) of a site is indisposed for a period and may need to delegate parts of his/her duties temporarily, e.g. to a sub-investigator. Any such changes should be documented in the site's source records. Any permanent changes in PI should be communicated to the sponsor.
- There may also be circumstances where immediate actions are required by the sponsor and/or investigator, outside of what is contemplated in the protocol, in order to protect a study participant from immediate hazard. Any such measures will be carefully documented and conducted in accordance with the National Competent Authority (NCA)/IRB/IEC regulations.

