Number of Participants: A total of 654 participants with a 2:1 randomization ratio to either CAB LA+RPV LA or BIK is such that the study has approximately 85% power to demonstrate non-inferiority in the proportion of participants with snapshot virologic failure at Month 12 using a 4% margin, assuming a true 2% failure rate for CAB LA + RPV LA and a 1% failure rate for the BIK arm using a 2.5% one-sided alpha level. The randomized portion of the study will continue for 12 months with an Extension Phase.

Intervention Groups and Duration:

IM Injections every 2 months (Oral Lead In):

Day 1 – CAB 30 mg + RPV 25 mg oral, administered once daily for 1 month

Month 1 – CAB LA 600 mg + RPV LA 900 mg IM, each given as 1 X 3 mL IM injection

Month 2 - CAB LA 600 mg + RPV LA 900 mg IM, each given as 1 X 3 mL IM injection

Month 4 and Q2M thereafter - CAB LA 600 mg + RPV LA 900 mg IM, every 2 months until Month 12, each given as 1 X 3 mL IM injection

IM Injections every 2 months (Direct to Injections):

Day 1- CAB LA 600 mg + RPV LA 900 mg IM, each given as 1 X 3 mL IM injection

[figure not shown]
Month 1 and Q2M thereafter- CAB LA 600 mg + RPV LA 900 mg IM, each given as 1 X 3 mL IM injection

BIC/FTC/TAF (BIK)

Day 1 – BIC 50 mg + FTC 200 mg + TAF 25 mg oral, administered once daily until Month 12.

Data Monitoring or Other Committee: No

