3. OBJECTIVES AND ENDPOINTS

Objectives	Endpoints
Primary	
To demonstrate the non-inferior antiviral activity of CAB LA + RPV LA every two months compared to a BIK single tablet regimen administered once daily over 12 months in suppressed HIV-1 infected antiretroviral therapy (ART)-experienced participants	Proportion of participants with plasma HIV-RNA greater than or equal to 50 copies/mL as per Food and Drug Administration (FDA) Snapshot algorithm at Month 12 (OLI and BIK)/Month 11 (D2I) (Intent-to-Treat Exposed [ITT-E] population)
Secondary	
To demonstrate the antiviral and immunologic response with the use of CAB LA + RPV LA every 2 months compared to a BIK single tablet regimen administered once daily	Proportion of participants with plasma HIV-1 RNA <50 c/mL (c/mL) at Month 6 and Month 12 (OLI and BIK)/Month 5 and Month 11 (D2I) using the FDA Snapshot algorithm (Intent-to-Treat Exposed [ITT-E] population)

Objectives	Endpoints
	
Proportion of participants with protocol-defined confirmed virologic failure (CVF) through Month 6 and Month 12 (OLI and BIK)/Month 5 and Month 11 (D2I).
 
Proportion of participants with HIV-RNA greater than or equal to 50 c/mL as per FDA Snapshot algorithm at Month 6, and Month 12 (OLI and BIK)/Month 5 and Month 11 (D2I)
 
Absolute values and changes from Baseline in viral load and CD4+ cell count over time including Month 6 and Month 12 (OLI and BIK)/Month 5 and Month 11 (D2I)

To assess viral resistance in participants experiencing protocol-defined confirmed virologic failure	Incidence of treatment emergent genotypic and phenotypic resistance to CAB, RPV, BIC, FTC, and TAF through Month 6 and Month 12 (OLI and BIK)/Month 5 and Month 11 (D2I).
To evaluate renal (in urine and blood) and bone (in blood) biomarkers in participants treated with CAB LA + RPV LA compared to BIK	Change from Baseline (Day 1) in renal and bone biomarkers at Months 6 and 12 (OLI and BIK)/Month 5 and Month 11 (D2I).
To evaluate Metabolic Syndrome for participants treated with CAB + RPV and BIK	Change from Baseline in proportions of participants with Metabolic syndrome at Months 6 and 12 (OLI and BIK)/Month 5 and Month 11 (D2I)
To evaluate insulin resistance in participants treated with CAB LA + RPV LA compared to BIK	Change from Baseline (Day 1) in homeostasis model of assessment-insulin resistance (HOMA-IR) at Months 6 and 12 (OLI and BIK)/Month 5 and Month 11 (D2I).

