6.9.1. IM Dosing

Participants receiving CAB LA and/or RPV LA are anticipated to be at risk for development of virologic resistance if ART is interrupted. The time period during which participants are at risk for development of virologic resistance may be determined by the period between when drug levels fall below therapeutic values and when they fall below levels which exert selective pressure on HIV. This time period will vary by ART agent and is dependent upon effective concentration, inhibitory concentration, and half-life. Plasma concentrations of both LA drugs may be measurable for more than one year following IM injections. Any interruption in IM dosing should be discussed with the Medical Monitor. Investigators should ensure that the participant initiates alternative highly active ART to minimize the risk of developing resistance as concentrations of CAB and RPV decline over time.

IM dosing is expected to occur during the week in which the participant's projected visit falls (as according to the date of the first injection). The first injections for participants who choose to start injections immediately will occur at Day 1. The first injections for participants electing to participate in the oral lead are administered at Month 1 (can be performed before lab results become available), and the second injections are given at Month 2.

The participant's projected visit is determined by their first injection date and, ideally, is the same date for every injection. For example, if the 1st dose (Month 1) is January 15th, then dose 2 (Month 2) will be February 15th, and dose 3 (Month 4) will be April 15th, etc.

Since the first injection visit (Day 1 or Month 1) will determine the future injection visit schedule for participants, planning for the first injection visit date (within allowed visit windows) should take into consideration the availability of the participants to adhere to future visit windows (planned vacations, business trips, weekends, holidays, *etc.*).

Dosing for participants randomized to CAB LA + RPV LA is as follows:

All injections should be planned as single injections per drug.

6.9.1.1. IM injections every 2 months (Oral Lead In):

Month 1 – CAB LA 600 mg + RPV LA 900 mg IM, each given as 1 X 3 mL IM injection

Month 2 - CAB LA 600 mg + RPV LA 900 mg IM, each given as 1 X 3 mL IM injection

Month 4 and Q2M thereafter - CAB LA 600 mg + RPV LA 900 mg IM, every 2 months until Month 12, each given as 1 X 3 mL IM injection

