7.1.5. Virologic Failure

Only plasma HIV-1 RNA values determined by the central laboratory will be used to assess virologic failure.

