9. STATISTICAL CONSIDERATIONS

9.1. Statistical Hypotheses

The study is to demonstrate the non-inferior antiviral activity of CAB LA + RPV LA every 2 months compared to a BIK single tablet regimen administered once daily over 12 months in suppressed HIV-1 infected antiretroviral therapy (ART)-experienced participants.

Non-inferiority can be concluded if the upper limit of a two-sided 95% confidence interval for the difference in proportion of participants with HIV-1 RNA ≥ 50 c/mL at Month 12 between the two treatment arms (CAB LA + RPV LA – BIK) is less than 4%.

Let p_c , p_b be the proportion of participants with HIV-1 RNA ≥ 50 c/mL in the CAB LA+RPV LA and BIK arms respectively, then the primary statistical hypothesis can be written as follows:

$$H_0: p_c - p_b \geq 4\% \text{ vs. } H_1: p_c - p_b < 4\%$$

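### The COVID-19 appendix does not protect the central HIV-1 RNA sample at Month 11/12 when an injection visit goes ahead without laboratory tests, and samples lost this way lean the primary comparison towards non-inferiority

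*Protocol*

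**What the plan says.** Protocol Section 10.11.1 sets out what may change at visits disrupted by the pandemic. Where it constrains site staff, "IM dosing visits may proceed with limited or no other protocol-defined assessments (e.g. lab tests, questionnaires, etc". Appendix 11 confines its measures to those needed "as a result of COVID-19 only". One test is kept by name: point-of-care pregnancy testing before an injection. HIV-1 RNA is not named. The only trigger for missed tests is this: "If lab tests will be missed for more than one consecutive visit, the medical monitor must be contacted, to provide guidance for safety monitoring". Local laboratory results may be used to inform safety decisions.

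The primary timepoint is an injection visit in the long-acting arm. Section 6.9.1 schedules oral lead-in participants "every 2 months until Month 12, each given as 1 X 3 mL IM injection", and direct-to-injection participants are dosed at Month 11. BIK is "oral, administered once daily until Month 12" (Section 1.1), so that arm has no injection visits in the randomized phase.

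The primary endpoint in Section 3 is "Proportion of participants with plasma HIV-RNA greater than or equal to 50 copies/mL as per Food and Drug Administration (FDA) Snapshot algorithm at Month 12" (Month 11 for direct to injection) in the ITT-E population. Section 9.3.1 defines that population as everyone randomized who took at least one dose. Section 9.1 judges non-inferiority on "the difference in proportion of participants with HIV-1 RNA" of 50 c/mL or more, with a 4% margin. Section 4.1 states missing, switch or discontinuation = failure for the key secondary endpoint below 50 c/mL. Section 7.1.5 adds: "Only plasma HIV-1 RNA values determined by the central laboratory will be used to assess virologic failure".

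**The concern.** The appendix protects one named test and leaves the primary-endpoint sample unprotected. A single missed Month 11/12 sample does not trigger contact with the Medical Monitor, because that needs more than one consecutive visit and is for safety monitoring. A local result is offered for safety decisions, not for efficacy. The repeat test in Section 7.1.7.1, due within 4 weeks and inside the same analysis window, follows only a measured value from 50 to below 200 c/mL. No draw is required when the value is simply absent, and the next scheduled injection visit is two months later.

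What is at stake is the direction of any loss. In a non-inferiority comparison of failure proportions, a participant who stays in the denominator but cannot enter the numerator makes the regimen look better. A statistical analysis plan can classify such participants, but it cannot recover blood that was never drawn. Only the protocol can ask for the draw.

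**Working it through.** **Inputs from the protocol (Section 9.2.1 and Table 7).** 436 long-acting and 218 BIK participants; margin 4%; one-sided 2.5%; design failure rates 2% and 1%; Miettinen-Nurminen score test.

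**Assumed, because the protocol gives no figure.** A share m of participants has no HIV-1 RNA value anywhere in the analysis window. Missingness is unrelated to outcome, and unmeasured participants stay in the denominator and are not counted as failures.

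**Step 1: reproduce the plan's power.** The test rejects when

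Z = (p̂c − p̂b − 0.04) / √{[p̃c(1 − p̃c)/436 + p̃b(1 − p̃b)/218] × 654/653} < −1.96,

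where p̃ are the estimates restricted to a difference of 4%. Summing exact binomial probabilities over the rejection region at 2% vs 1% gives 85.1%, against about 85% stated. The other rows of Table 7 give 81.1% (stated 80%) and 90.8% (stated 90%).

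**Step 2: effect of m on the apparent rate.** Apparent rate = true rate × (1 − m). With a true difference exactly at the margin, 5% vs 1%, and loss in the long-acting arm only:

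- m = 3%: 5% × 0.97 = 4.85%, apparent difference 3.85 points
- m = 5%: 5% × 0.95 = 4.75%, apparent difference 3.75 points
- m = 10%: 5% × 0.90 = 4.50%, apparent difference 3.50 points

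**Step 3: one-sided error, long-acting arm only.**

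| True rates | m = 0 | 3% | 5% | 10% |
|---|---|---|---|---|
| 5% vs 1% | 2.38% | 3.13% | 3.75% | 5.79% |
| 6% vs 2% | 2.52% | 3.31% | 3.95% | 6.07% |

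**Step 4: equal loss in both arms.** At 5% vs 1%, the error is 3.45% with 5% missing and 4.95% with 10% missing. At 6% vs 2% with 10% missing it is 4.57%. Equal loss does not remove the effect, because it shrinks the absolute difference as well.

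**Step 5: other test form.** Section 9.4.1 plans a stratified CMH difference with a normal-theory interval, not the score test. An unstratified normal-theory test gives 2.53%, 4.02% and 6.26% at m = 0, 5% and 10% (5% vs 1%, long-acting arm only), so the pattern does not depend on the choice of test.

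**Step 6: scale at the design rate.** With a true 2% rate and m = 10%, expected failures hidden = 436 × 0.02 × 0.10 = 0.87. Apparent power moves from 85.1% to 90.7%.

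**The case against.** Several counter-arguments have weight.

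- **Extension entry.** Sections 2.1 and 6.3.1 tie Extension entry to a viral load below 50 c/mL at Month 11/12 or on retest, so a site has a practical reason to draw the sample. This stands as a brake. However, Section 4.1.3.1 does not repeat the condition for the long-acting arm, and Appendix 11 does not connect it to the waiver.
- **Later draw.** Section 7.1.7.1 shows that a sample up to 4 weeks after the visit can fall in the same window, so an omitted visit sample is not yet a missing endpoint. This stands too. Such a draw is possible, but nothing requires it.
- **Conditional waiver.** It applies only to documented COVID-19 impact with constrained staff, and the affected share may be very small.
- **Visibility.** The secondary endpoint counts missing as failure. A 10% loss in the long-acting arm alone would cost about 0.10 × 0.98 = 9.8 points there, against a −12% margin, so heavy loss would show. That does not restore the error rate of the primary test.
- **Central laboratory.** Section 7.1.5 concerns protocol-defined virologic failure, which Section 7.1.6 defines for clinical management, and does not expressly govern the Snapshot endpoint. Section 8.2.2 does, however, require scheduled laboratory assessments to be done centrally.

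Two stronger readings are tempting. A reader might infer that an unmeasured viral load can never count as a failure in the primary analysis. The protocol does not say so: it follows only by inference from the endpoint definition, the ITT-E denominator and the placement of missing = failure, and detailed data handling may sit in the analysis plan. A reader might also infer that the loss falls on the long-acting arm alone. The injection-visit waiver does reach only that arm, but Section 10.11.1 also foresees reduced on-site visits and Section 10.11.4 allows shipment of oral medication, so BIK samples may be lost as well.

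**Conclusion.** The point holds as a gap in the protocol text. Under COVID-19 staff constraint, the central Month 11/12 HIV-1 RNA sample may be skipped at an injection visit, and no make-up draw is required. The likely direction of the resulting bias is towards non-inferiority.

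The size cannot be fixed from the document. It is small if few samples are lost (error 2.4% to 3.1% at 3%) and material at 10% (5.8% if the loss is in the long-acting arm only, about 5.0% if in both arms). These figures assume that values are missing for the whole window, at random, with unmeasured participants kept as non-failures, and true rates at the margin. They are scenarios and do not predict how much was or will be lost. The point justifies a cheap clarification. It does not show that the primary analysis is invalid.

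**What to change.** Add to Section 10.11.1 that the central HIV-1 RNA sample at Month 11 (direct to injection) or Month 12 (oral lead-in), and any required retest, is to be prioritised and not omitted when the participant is seen in person. If it is missed, a central sample must be drawn within the same analysis window. Give the BIK Month 12 visit the same priority. State that the sample is not a condition for giving the injection, so that the dosing provisions of the appendix are unchanged.

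Extending this to Month 5/6, and reporting by arm how many participants lack a Month 11/12 value for COVID-19 reasons, would be useful but is optional.

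The cost is a sentence or two in the appendix, one blood tube that is already scheduled, and slightly less flexibility for a constrained site.
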